16.2.2.	Training.....	71
16.2.3.	Compliance.....	71
16.2.4.	Source data verification.....	72
16.2.5.	IMP.....	72
16.3.	Responsibilities of the Data Manager.....	72
17.	ETHICS AND REGULATORY CONSIDERATIONS.....	72
18.	AUDIT AND INSPECTION.....	73
19.	REFERENCE.....	74

List of abbreviations and definition of terms

aPTT	Activated Partial Thromboplastin Time
AE	Adverse Event
ANOVA	ANalysis Of VAriance
ATC	Anatomical Therapeutic Chemical
CRF	Case Report Form
CRO	Contract Research Organisation
CSP	Code de la Santé Publique
CV	Curriculum Vitae
D	Day
DSMB	Data and Safety Monitoring Board
EC	Ethics Committee
FAS	Full Analysis Set
FFP	Fresh Frozen Plasma
FIGO	International Federation of Gynecology and Obstetrics
FU	Follow-up
GCP	Good Clinical Practice
h	Hour
HAS	Haute Autorité de Santé
Hb	Haemoglobin
HES	Hydroxyethylstarch
Ht	Haematocrit
ICH	International Conference on Harmonisation of Technical Requirements for Registration of Pharmaceuticals for Human Use
ICM	International Confederation of Midwives
IEC/IRB	Independent Ethics Committee (IEC) or International Review Board (IRB)
IMP	Investigational Medicinal Product
IV	IntraVenous
LDH	Lactate DeHydrogenase
LFB	Laboratoire français du Fractionnement et des Biotechnologies
LLT	Lowest Level Term
LMWH	Low-Molecular-Weight Heparin
LOCF	Last Observation Carried Forward
MedDRA	Medicinal Dictionary for Regulatory Activities
min	Minute
NA	Not Applicable
NCR	No Carbon Required
ND	Not Done
PCC	Prothrombin Complex Concentrates
PICU	Post Interventional Care Unit
PPH	Post-Partum Hemorrhage
PT	Preferred Terms
PT	Prothrombin Time
QT	Quick's Test
RBC	Red Blood Cells

rFVIIa	Recombinant activated Factor VII
SAE	Serious Adverse Event
SAP	Statistical Analysis Plan
SOC	System Organ Class
SPC	Summary of Product Characteristics
SOFA	Sequential Organ Failure Assessment
TRALI	Transfusion-Related Acute Lung Injury
UNK	UNKnown
VBL	Volume of Blood Loss
WHO	World Health Organization

SYNOPSIS

TITLE
	
A randomised, multicentre, double-blind, placebo-controlled study on the efficacy and safety of a therapeutic strategy of post-partum haemorrhage comparing early administration of human fibrinogen versus placebo in patients treated with intravenous prostaglandins following vaginal delivery.
 
Short title: Fibrinogen in haemorrhage of DELivery: FIDEL

SPONSOR
	
LFB BIOMEDICAMENTS [name] [name]


COORDINATING INVESTIGATOR / SCIENTIFIC COMMITTEE
	
Coordinating Investigator:    e  
 
Scientific Committee:     

INVESTIGATIONAL MEDICINAL PRODUCT (IMP) AND ASSOCIATED TREATMENTS
	
Investigational medicinal products (IMP): The participants are assigned to either:
 
 ○ Fibrinogen (Clotfact[®]): 3g (2 vials of 1.5g/100 ml) or, ○ Placebo: 2 vials of 100 ml 
Route of administration:
 
 ○ As soon as possible during the 30 minutes following the start of prostaglandin infusion ○ Intravenous (IV) administration with a flow rate ≤ 20 ml/min 
Treatment allocation:
 
 ○ The treatment will be double-blind. ○ Randomisation will be stratified on the centre. ○ Each treatment unit contains 2 vials of powder and 2 solvent vials of 100 ml. ○ Treatment units will be numbered and will be allocated in chronological order of inclusion by ascending number.

	
Associated treatments:
 
 ○ IMP is administered as soon as possible after start of prostaglandin infusion. The dose of prostaglandin will be administered according to the 2004-recommendations provided by the French National Authority for Health (Haute Autorité de Santé, or HAS). ○ Following the administration of IMP, the therapeutic management will be totally left to the discretion of the investigator. ○ However, some concomitant treatments will be administered in accordance with the following recommendations: ○ Fibrinogen concentrate as rescue therapy: if administered, it will not be administered: 
 ▪ within 60 minutes following the start of IMP administration, 
OR
 
 ▪ before at least 2 units of packed RBCs have been administered to the patient. 
 ○ Tranexamic acid: 
 ▪ The administration of tranexamic acid will be allowed only after prostaglandin infusion has been decided. ▪ Recommended dose: 1 g IV to be renewed once after 30 min. ○ Transfusional strategy: in accordance with the following objectives: 
 - Hemoglobin (Hb) \geq 8 g /100 ml, - PT \geq 40%, - Platelets count \geq 50 000/mm³, 
Transfusions of red blood cells (RBC), fresh frozen plasma (FFP) and platelets units can be performed before availability of laboratory results, when indicated.
 ○ Hydroxyethylstarch (HES): maximum dose of 1.5 L during the first 24 hours.
STUDY DESIGN	Phase IV multicentre, randomised, double-blind, placebo-controlled, parallel-group study
OBJECTIVES	
Primary:
 
 ● To assess the benefits of a therapeutic strategy that associates an early administration of human fibrinogen concentrate in the management of PPH on the reduction of bleeding after the initiation of prostaglandins intravenous infusion. 
Secondary:
 
 ● To assess the evolution of haemorrhage ● To assess the need for haemostatic intervention ● To assess the need for intrauterine balloon

	
 • To assess the maternal morbi-mortality • To assess the biological effects of fibrinogen concentrate administration • To assess the tolerance of fibrinogen concentrate administration
NUMBER OF PATIENTS	
It is estimated that, in the control group, 42% of patients will fulfill the primary endpoint. With an expected percentage of patients in the Clotfact[®]-treated group of 27%, the difference between the two groups will be 15%. With a power (1-β) = 90%, an α risk-error = 5% and a two-sided test (Z test, unpooled variance), a sample size of 412= 2x206 evaluable patients is needed per group of treatment. Assuming a 5% rate of dropouts, about 434 patients are planned to be randomized in the study.
 
As there is some uncertainty about the test Z variance depending itself on the expected rates, the variance will be re-estimated in a blind way at 80% of the initially planned sample size and the sample size will be increased according to the new estimated variance so as to maintain the power to 90% while still considering the same originally planned difference in failure rates, i.e. 15%. It can be shown that the possible increase in sample size (after adjusting for drop-outs) cannot exceed 50 additional patients. Hence the reestimated sample size will not exceed 484 patients.

STUDY POPULATION (ELIGIBILITY CRITERIA)	
Inclusion criteria:
 
 • Signed and dated informed consent form • Vaginal delivery • PPH requiring IV administration of prostaglandins • At least one available result of Hb level during the third trimester of pregnancy • 18-year-old female patients and older • Covered by healthcare insurance in accordance with local requirements 
Non-inclusion criteria:
 
 • Caesarean section • Haemostatic intervention (as ligation, embolization or hysterectomy) already decided at the time of inclusion • Known placenta praevia or accreta • Hb level < 10g/dl during the third trimester of pregnancy • History of venous or arterial thromboembolic event • Known inherited bleeding or thrombotic disorders • Treatment with low-molecular-weight heparin (LMWH) within 24 hours prior to the inclusion • Treatment with acetylsalicylic acid within 5 days prior to the inclusion • Treatment with vitamin K antagonists within 7 days prior to the inclusion • Administration of fibrinogen concentrate within 48 hours prior to the

	
inclusion
 
 • Administration of FFP, platelets units or prohaemostatic drugs, tranexamic acid and rFVIIa or prothrombin complex concentrates (PCC) within 48 hours prior to the inclusion • Administration of RBCs within 3 months prior to the inclusion • Participation in another interventional clinical study using an investigational medicinal product within 30 days prior to the inclusion • Previous inclusion/enrolment in the present clinical study • Known history of hypersensitivity or other severe reaction to any component of Clottafact[®] or placebo • Minors, majors under guardianship, persons staying in health or social institutes and people deprived of their freedom • Known drug or alcohol abuse • Patients whose use of concomitant medication may interfere with the interpretation of data • Any other current significant medical condition that might interfere with treatment evaluation according to the investigator's judgement • Patients who are unlikely to survive through the treatment period and evaluation • Patients transferred from another service after the delivery
DURATION OF PATIENT PARTICIPATION	6 ± 2 weeks after the delivery
DATES OF BEGINNING AND END OF STUDY	
 • Planned date of inclusion of first patient: December 2013 • Planned date of last patient out: August 2018 at the latest
STUDY DESCRIPTION	
Consent: Informed consent will be obtained through an emergency procedure.
 
Inclusion:
 
 • Will take place after signing the emergency informed consent and checking the eligibility criteria. • Blood sampling n° 1 for biological data at inclusion. 
Randomisation:
 
 • Will be stratified on the centre. • The start of IMP administration corresponds to H0 (D0). • Recording of the time (start, end) of IMP infusion, 
H2 (120 ± 30 min): Blood sampling n° 2.
 
H6 (360 ± 30 min):
 
 • Blood sampling n° 3.

	
Morning of D2:
 
 • Blood sampling n° 4. 
Hospital discharge:
 
 • Parameters of therapeutic management and events that occurred during the admission in an ICU, including maximum SOFA score (if applicable), • PPH management summary 
At 6 ± 2 weeks following delivery:
 
Collection of tolerance data on the IMP during an obstetrical follow-up visit or a phone contact.

DESCRIPTION OF AND JUSTIFICATION FOR DATA COLLECTED
	
Anamnestic parameters:
 
 • Demographic parameters: height, weight prior to pregnancy and last known weight, • History of thromboembolic, obstetrical events and any clinically relevant medical conditions. • Obstetrical parameters of the pregnancy, mainly: 
 ○ Date of last menstrual period, gestational age, levels of Hb of the third trimester of pregnancy, ○ Ht and platelets will be collected if available. 
Delivery parameters:
 
 • Times of the start and the end of delivery and number of live births and/or stillbirths, • Start and end hours of haemorrhage, • Initial obstetrical management of the haemorrhage : artificial delivery, uterine or genital examination, • Any haemostatic intervention (intrauterine balloon, uterine ligation, embolization, vascular ligation, hysterectomy), • Vascular filling (if any): volumes and types of filling solutes since the start of delivery until D2, • Transfusions: types and number of transfused blood products since the start of delivery. 
Clinical events until hospital discharge:
 
 • Duration of stay in the obstetrics room (arrival and discharge hours), • Number of days of hospital stay following delivery, • Number of days in resuscitation and/or intensive care and/or PICU and/or continuous care units, • Number of days with assisted ventilation, • Maximum SOFA score for patients transferred in resuscitation and/or intensive care and/or PICU and/or continuous care units,

	
 • Renal failure requiring dialysis, • Hypotension episodes that required continuous vasopressor therapy, • Acute pulmonary oedema, acute respiratory distress syndrome, transfusion-related acute lung injury (TRALI), • Measured and/or estimated volumes of total blood loss, • Blood-collecting containers (if any): date, time and duration of setting and removal, 
Adverse events during the study
 
 • From the signature of the informed consent form to the end of study visit (6 ± 2 weeks after delivery): serious and non-serious AEs whether or not considered to be causally related to the investigational medicinal product (IMP). 
Laboratory parameters (at inclusion, H2, H6, D2):
 
 • Complete blood count, Hb, Ht and platelets • Plasma fibrinogen • Haemostatic profile: PT, QT, aPTT, D-dimers • Plasma creatinine and urea at inclusion and D2 
Prior/Concomitant treatments (total dose, modalities, start and end of administration):
 
 • Prior treatment: all relevant prior medication taken within 7 days before inclusion, including all medication administered since the beginning of the delivery • Concomitant treatments including intravenous fluids, blood products, tranexamic acid and fibrinogen concentrate as rescue therapy

ENDPOINTS AND EVALUATION PARAMETERS
	
Primary endpoint:
 
Percentage of patients losing at least 4 g/dl of Hb, and/or requiring the transfusion of at least 2 units of packed RBCs within the 48 hours following the administration of IMP.
 
The reference for Hb level is the most recent value recorded during the third trimester of pregnancy.
 
Secondary endpoints:
 
 • Evolution of haemorrhage 
 ○ Percentage of patients losing at least 4 g/dl of Hb, 48 hours following the IMP administration, with regards to the Hb reference level. ○ Percentage of patients losing at least 3 g/dl of Hb, 48 hours following the IMP administration, with regards to the Hb reference level. ○ Percentage of patients requiring transfusion of at least 2 units of packed RBCs, 48 hours following the IMP administration. ○ Percentage of patients losing at least 4 g/dl of Hb, 48 hours

	
following the IMP administration, with regards to the level of Hb measured at inclusion.
 
 ○ Percentage of patients with an occurrence of Hb level < 9 g/dl within the 48 hours period following inclusion. ○ Number of units of transfused blood products within the 48 hours period following IMP administration. ○ Calculated volume of total blood loss, 48 hours following the IMP administration. 
 ● Need for haemostatic intervention 
 ○ Percentage of patients requiring at least one of the following interventions within 48 hours following the IMP administration: uterine ligation (B Lynch or other techniques), pelvic arteries embolization, surgical vascular ligation, administration of rFVIIa and hysterectomy. ● Need for intrauterine balloon 
 ○ Percentage of patients requiring the use of intrauterine balloon within 48 hours following the administration of IMP. ○ Time of intrauterine balloon placement. ● Maternal morbi-mortality 
 ○ Length of stay in resuscitation and/or intensive care and/or post interventional care units (PICU) and/or continuous care. ○ Duration of admission in obstetrics unit. ○ Single or multi-organ failure (SOFA score) in case of transfer to resuscitation and/or intensive care and/or PICU and/or continuous care units. ○ Death during the study. ● Biological effects of fibrinogen concentrate administration 
 ○ Evolution of blood fibrinogen level and hemoconcentration between H0 (start of IMP infusion) and D2. ● Tolerance of fibrinogen concentrate administration 
 ○ Serious and non-serious adverse events (AE).

STATISTICS
	
The distribution of parameters will be summarised using descriptive statistics according to the study variable:
 
 ● Quantitative variables will be presented by their mean, standard deviation, standard error, median, quartiles and range, minimum and maximum values. The number of documented values will also be mentioned. ● Categorical variables (binary, nominal and ordinal) will be presented by contingency tables (frequencies and percents). Number and percentages of missing data will also be mentioned. 
All statistical tests will be two-sided with a threshold of statistical significance of 0.05.
 
The statistical analysis will be carried out according to the Intent-to-Treat (ITT) principle, depending on the group of randomisation regardless of the received treatment.
 
A per-protocol analysis will be carried out on the subgroup of patients with

	
no major protocol deviation if the per-protocol set represents less than 80% of the ITT set.
 
Unless otherwise specified, the following statistical tests will be used:
 
 • Categorical data will be compared using chi-square test or Fisher exact test if a theoretical number of one category or more is below 5. • Continuous quantitative data will be compared by t test or, if normality of distribution is rejected, by Wilcoxon non parametric test. 
No subgroup analysis is planned.
 
The primary analysis will be conducted in the ITT set. Missing data will not be replaced in the primary analysis.
 
The primary model of analysis will be an exact logistic regression adjusting for treatment, centre, and baseline fibrinogen (categorized into three classes, $\leq 2 \text{ g L}^{-1}$, $] 2 \text{ g L}^{-1} - 4 \text{ g L}^{-1}$], $> 4 \text{ g L}^{-1}$).
 
The treatment effect (odds ratio of failure) with its 95% confidence interval will be estimated in this model.
 
The same analysis proposed will be performed in the ITT and PP sets.
 
Sensitivity analyses replacing missing data with failures regardless of the treated group will be implemented.
 
Analysis of tolerance will be carried out on women at least one dose of IMP.
 
No interim analysis is planned.

--	---------------------------------------------------------------------------------------------------------------------------------------------------------------------------------------------------------------------------------------------------------------------------------------------------------------------------------------------------------------------------------------------------------------------------------------------------------------------------------------------------------------------------------------------------------------------------------------------------------------------------------------------------------------------------------------------------------------------------------------------------------------------------------------------------------------------------------------------------------------------------------------------------------------------------------------------------------------------------------------------------------------------------------------------------------------------------------------------------------------------------------------------------------------------------------------------------------------------------------------------------------------------------------------------------------------------------------------------------------------------------------------------------------------------------------------------------------------------

STUDY FLOW-CHART (Table 1)

ETUDE FIDEL	CONSENT FORM	INCLUSION	TREATMENT	FOLLOW-UP				END OF STUDY
	Visit 1 Inclusion Blood sampling 1		Visit 2 Randomisation IMP infusion	Visit 3 Blood sampling 2	Visit 4 Blood sampling 3	Visit 5 Morning of D2 Blood sampling 4	Visit 6 Hospital discharge	Visit 7
	Before H0		H0 = start of IMP infusion*	H2 (120 ± 30 min)	H6 (360 ± 30 min)			6 ± 2 weeks after delivery
Informed consent	x							
Inclusion/exclusion criteria	x	x						
Demographics		x						
Medical history (including thromboembolic and obstetrical events and any clinically relevant medical condition)		x						
Pregnancy parameters		x						
Delivery parameters		x						
Clinical exams								
PPH parameters		x	x	x	x		x	
Physical examination		x					x	
Vital signs (arterial pressure, heart rate)		x		x	x	x	x	
Stay in ICU data (if applicable)								
SOFA score maximum**							x**	
Laboratory tests								
Biochemical tests (plasmatic creatinine and urea)		x				x		
Coagulation tests (fibrinogen, PT, QT, aPTT, D-dimers)		x		x	x	x		
Haematological tests (CBC, Hb, Ht, Plt)		x		x	x	x		

ETUDE FIDEL	CONSENT FORM	INCLUSION	TREATMENT	FOLLOW-UP				END OF STUDY
		Visit 1	Visit 2	Visit 3	Visit 4	Visit 5	Visit 6	Visit 7
Treatments								
Prior treatments		x						
Concomitant treatments		x	x	x	x	x	x	x
Resuscitation fluids		x	x	x	x	x		
Transfusions of blood products		x	x	x	x	x	x	x
IMP								
Reconstitution			By a third party					
Administration			H0*					
Adverse event collection			x	x	x	x	x	x

* Start of IMP infusion should be within the 30 min following the start of prostaglandin infusion and at a flow rate ≤ 20 ml/min

** SOFA score will be assessed only for patients transferred in an Intensive Care Unit

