8.2.2. Visit 2: Randomisation and IMP infusion

- Randomisation will be performed as soon as possible after inclusion and after the start of prostaglandins infusion (see Section 8.1.3).
- IMP administration
 - A third party reconstitutes the IMP (see [Section 6.4.2](#)).
 - The start of IMP infusion corresponds to H0 and should be within the 30 minutes following the start of prostaglandins infusion.
 - The start and the end times and the administered volume will be collected in the CRF.
- Concomitant treatments including intravenous fluids and blood products;
- Local tolerance which occurred during IMP infusion and AEs if any.

8.2.3. Visit 3: H2 (120 ± 30 min) / Blood sampling 2

The following data will be collected in the CRF:

- Blood sampling:
 - Complete blood count, Hb, Ht, platelets,
 - Haemostatic profile: fibrinogen, PT, QT, aPTT, D-dimers,
- Vital signs
 - Measurement of arterial blood pressure (systolic and diastolic),
 - Heart rate;
- Haemorrhage parameters:
 - Measured or estimated volume of blood loss from the start of bleeding;
- Concomitant treatments including intravenous fluids, blood products, tranexamic acid and fibrinogen concentrate as rescue therapy: any modification or institution of a new treatment;
- AEs if any.

8.2.4. Visit 4: H6 (360 ± 30 mn) / Blood sampling 3

[figure not shown]
The following data will be collected in the CRF:

- Blood sampling:
 - Complete blood count, Hb, Ht, platelets,
 - Haemostatic profile: fibrinogen, PT, QT, aPTT, D-dimers,
- Vital signs
 - Measurement of arterial blood pressure (systolic and diastolic);
 - Heart rate;
- Haemorrhage parameters:
 - Measured or estimated volume of blood loss from the start of bleeding;
- Concomitant treatments including intravenous fluids, blood products, tranexamic acid and fibrinogen concentrate as rescue therapy: any modification or institution of a new treatment;
- AEs if any.

8.2.5. Visit 5: morning of D2 / Blood sampling 4

Depending on the time of delivery, the assessment in the morning of D2 may differ from H48 (considering that the first blood sampling in hospital is performed around 7h00 in the morning).

H0 = start of IMP administration

Even if the patient has been transferred to another hospital or department within the same hospital, the investigator must ensure that all laboratory analyses will be performed, and the following parameters will be recorded in the CRF:

- Blood sampling:
 - Complete blood count, Hb, Ht, platelets,

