No interim analysis is planned.

12.10.1. 3. *Secondary efficacy variables*

Analyses of secondary efficacy endpoints will be primarily conducted in the ITT set. Sensitivity analyses will be performed in the PP set. Missing data will not be replaced.

12.10.1. 3.1. Description of secondary efficacy variables

Secondary efficacy variables are listed in [Section 10.1.2](#).

The following parameters will also be derived:

1. Change in plasma fibrinogen level (g/L) between H2 and H0
2. Change in plasma fibrinogen level (g/L) between H6 and H0
3. Change in plasma fibrinogen level (g/L) between D2 and H0
4. The same changes will be calculated for Hb, Ht and RBCs
5. Duration of haemorrhage (hours): end time of haemorrhage – start time of haemorrhage
6. Length of stay in the obstetrics room (arrival and discharge hours)
7. Length of stay in obstetrics units (date of delivery and discharge date)
8. Number of days in resuscitation and/or intensive care and/or PICU and/or continuous care units (admission date and discharge date)
9. Number of days with assisted ventilation

12.10.1. 3.2. Analysis of secondary efficacy variables

Otherwise specified thereafter, all secondary efficacy variables will be compared between the 2 groups using chi-square for categorical data and using t test for continuous quantitative data or other appropriate tests.

Raw laboratory variables (including baseline data) will be presented by randomisation group at each determination (H0, H2, H6 and D2) and shift tables will also be displayed at the same periods. No statistical test will be performed on those data. Determinations at other sampling times will be listed except if other specific times are defined in the SAP.

Changes in laboratory parameters will be presented by randomization group and t test will be performed to test the hypothesis H0: no difference between the 2 randomization groups versus H1: any difference between the 2 randomization groups.

Furthermore, will be compared by t test in the subgroup of patients transferred in resuscitation and/or intensive care and/or PICU and/or continuous care units:

1. Number of days in resuscitation and/or intensive care and/or PICU and/or continuous care units,
2. Number of days with assisted ventilation.

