1.10.2 Secondary endpoints

1.10.2.1 Evolution of haemorrhage

- Percentage of patients losing at least 4 g/dL of Hb within 48 hours following IMP administration with regards to the Hb reference level.
- Percentage of patients losing at least 3 g/dL of Hb within 48 hours following IMP administration with regards to the Hb reference level.
- Percentage of patients requiring the transfusion of at least 2 units of RBCs within 48 hours following IMP administration.
- Percentage of patients losing at least 4 g/dL of Hb within 48 hours following IMP administration with regards to the level of Hb measured at inclusion.
- Percentage of patients with an occurrence of Hb level < 9 g/dl within 48 hours following IMP administration.
- Number of units of transfused blood products within 48 hours following IMP administration.
- Calculated volume of total blood loss, 48 hours following IMP administration.

The calculation and adjustment of total blood loss with regards to transfusional needs will be calculated at time of statistical analysis as follows:

- Total blood loss (mL) = blood loss calculated + blood loss compensated by transfusion
- Calculated blood loss: Pregnancy total blood volume x (Ht0 – Htf) x (100/35)
 - Pregnancy total blood volume = (Maternal weight measured before pregnancy x 65 mL/kg) x 1.4
 - Ht0: last available value of haematocrit before delivery
 - Htf: value of haematocrit in the morning of D2

Blood loss compensated by transfusion (mL): n RBC x 500mL (with n corresponding to the number of transfused units and 500mL = total transfused blood volume of 300 mL RBC with Ht of 60%).

1.10.2.2 *Need for haemostatic intervention*

- Percentage of patients requiring at least one of the following interventions within 48 hours following IMP administration of: pelvic arteries embolization, surgical vascular ligation, uterine ligation (B Lynch or other techniques), administration of recombinant activated Factor VII (rFVIIa) and hysterectomy.

1.10.2.3 *Need for intrauterine balloon*

- Percentage of patients requiring the use of intrauterine balloon within 48 hours following the administration of IMP.
- Time of intrauterine balloon placement.

1.10.2.4 *Maternal morbi-mortality*

- Length of stay in resuscitation and/or intensive care and/or post interventional care units (PICU) and/or continuous care.
- Length of stay in obstetrics units.

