- 1- Change in plasma fibrinogen level (g/L) between H2 and H0
- 2- Change in plasma fibrinogen level (g/L) between H6 and H0
- 3- Change in plasma fibrinogen level (g/L) between D2 and H0
- 4- The same changes will be calculated for Hb, Ht and RBCs
- 5- Duration of haemorrhage (hours): end time of haemorrhage – start time of haemorrhage

- 6- Duration in the obstetrics room (from arrival hour in obstetrics room to delivery hour)
- 7- Duration of hospitalization (from arrival date in obstetrics room to hospital discharge date)
- 8- Number of days in resuscitation and/or intensive care and/or PICU and/or continuous care units (admission date and discharge date)
- 9- Number of days with assisted ventilation

3.3.6.3.2 *Analyses of secondary efficacy variables*

3.3.6.3.2.1 Analyses of key secondary variables

The analyses of key secondary variables will be tested with the Hochberg step-up method:

- 1- Calculated/estimated volume of total blood loss, 48 hours following IMP administration

The estimated/calculated volume of total blood loss 48 hour after IMP administration will be compared between the Clottafact[®] group and placebo group by a t test or non parametric test.

- 2- Percentage of patients requiring any need for rescue procedure

The percentage of patients requiring any need for rescue procedure within 48 hours following IMP administration will be calculated and chi-square or Fisher exact tests will be used to compare between the Clottafact[®] group and placebo group.

- 3- Percentage of patients requiring the use of intrauterine balloon within 48 hours following IMP administration

The percentage of patients requiring the use of intrauterine balloon within 48 hours following the administration will be calculated and chi-square or Fisher exact tests will be used to compare between the Clottafact[®] group and placebo group.

3.3.6.3.2.2 Other analyses of secondary variables

Other secondary endpoints will be analysed in an exploratory purpose.

3.3.6.3.2.2.1 Analyses of the change from baseline in plasma fibrinogen level, Hb and Ht

The evolution in plasma fibrinogen level, Hb and Ht will be analysed at H2, H6 and D2 following IMP administration with a Mixed Model of Repeated Measurements comparing the Clottafact[®] group and placebo group.

3.3.6.3.2.2.2 Analyses of the evolution of haemorrhage

3.3.6.3.2.2.2.1 Analyses of haemoglobin level

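### The SAP starts the hospital-stay clock at arrival in the obstetrics room, not at delivery: an unlisted change that lets pre-randomisation days into an exploratory outcome for some women and leaves the protocol's variable unanalysed

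*Protocol*

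**What the plan says.** **Protocol.** The synopsis list of clinical events to be collected includes "Number of days of hospital stay following delivery". Section 12.10.1.3.1 item 7 gives the only explicit derivation: "Length of stay in obstetrics units (date of delivery and discharge date". Both start at delivery. The synopsis endpoint list calls the endpoint a duration of admission and gives no start point; Sections 3.2.2.4 and 10.1.2 name a length of stay without start or end.

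**SAP.** Section 1.10.2.4 keeps the endpoint name "Length of stay in obstetrics units", again without start or end. In the list of derived variables (3.3.6.3.1), item 7 reads "Duration of hospitalization (from arrival date in obstetrics room to hospital discharge date". Section 6.3, which defines several durations, does not define this one. The secondary-analyses row of the table of changes in 2.2 covers only the repeated-measures model; no row mentions the stay variable.

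**Status and population.** For variables outside the three key secondary ones, the SAP states: "Other secondary endpoints will be analysed in an exploratory purpose". Section 3.3.6.3.2.2.4 analyses duration of hospitalisation in women transferred to resuscitation, intensive care or similar units. Table 14.2.5.5.2 in the SAP table list is labelled for the ITT set.

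**The concern.** Women are randomised after they have delivered and after treatment for the bleeding has begun. A clock that starts at arrival in the obstetrics room counts time that was complete before the treatments could differ. That time adds variation without any treatment signal. The reported result would also not be the quantity the protocol defined, and a reader of SAP 2.2 would not learn of the switch. At stake are the precision of one exploratory morbidity comparison and its agreement with the protocol.

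**Working it through.** **1. Definitions side by side**

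| Source | Start | End |
|---|---|---|
| Protocol synopsis, data collected | delivery | end of hospital stay |
| Protocol 12.10.1.3.1 item 7 | date of delivery | discharge date |
| Protocol synopsis, endpoint list | not stated | not stated |
| SAP 1.10.2.4 | not stated | not stated |
| SAP 3.3.6.3.1 item 7 | arrival date in obstetrics room | hospital discharge date |

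The two item 7 entries hold the same place in parallel lists. No other SAP analysis or table runs from delivery to discharge.

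**2. Where the added time lies.** Patients must have had a vaginal delivery with haemorrhage needing IV prostaglandins (Protocol 5.2.1), and those transferred in after delivery are excluded (5.2.2, criterion u). Protocol 8.2.2 adds: "Randomisation will be performed as soon as possible after inclusion and after the start of prostaglandins infusion". The order is therefore arrival, delivery, bleeding, prostaglandins, randomisation. All arrival-to-delivery time precedes randomisation.

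**3. Effect on the treatment difference.** Write the SAP variable as T = A + S, where A is days from arrival to delivery and S is days from delivery to discharge. Over all randomised patients A has the same expected value in both arms, so the expected difference in T equals that in S. There is no bias. In the transferred subgroup, which is formed after randomisation, balance in A is not guaranteed.

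**4. Effect on variance (illustration).** The documents give no figure for this endpoint, so there is none to reproduce. Assumptions, none taken from the documents:

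- T is counted in dates, so A is 0 or 1 day, with probability q = 0.3 to 0.5 of being 1.
- The SD of S is 1 to 3 days.
- A and S are independent.

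Then Var(A) = q(1 − q), which is 0.3 × 0.7 = 0.21 or 0.5 × 0.5 = 0.25. The inflation factor is f = 1 + q(1 − q)/SD², and the equivalent loss of sample for a comparison of means is 1 − 1/f.

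| SD of S (days) | f at q = 0.3 | f at q = 0.5 | Equivalent sample loss |
|---|---|---|---|
| 1 | 1 + 0.21/1 = 1.21 | 1 + 0.25/1 = 1.25 | 17% to 20% |
| 2 | 1 + 0.21/4 = 1.053 | 1 + 0.25/4 = 1.063 | 5% to 6% |
| 3 | 1 + 0.21/9 = 1.023 | 1 + 0.25/9 = 1.028 | 2% to 3% |

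The mean stay would be longer by q, that is 0.3 to 0.5 day, in both arms alike.

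**5. The same in power.** Take an effect with 80% power on S. Power on T is Φ((1.960 + 0.842)/√f − 1.960). This gives 70.7% at f = 1.25, 77.6% at f = 1.063 and 78.9% at f = 1.028.

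**The case against.** **The protocol is not uniform.** Its synopsis endpoint label speaks of admission, which could suggest a clock starting at admission, and the synopsis entry that counts from delivery is a data-collection item about hospital stay rather than obstetrics units. This stands, so one cannot say that the protocol fixes the start at delivery everywhere. But its only explicit derivation of the endpoint starts at delivery, and the data item agrees.

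**The protocol also has a stay that starts at arrival.** Item 6 of the same list is "Length of stay in the obstetrics room (arrival and discharge hours". That is the obstetrics-room stay, a different variable. The SAP changes its end point too ("Duration in the obstetrics room (from arrival hour in obstetrics room to delivery hour"), which is a separate matter.

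**SAP item 7 may be a new variable for total hospitalisation.** If so, the protocol's delivery-to-discharge variable has been dropped without notice, so reconciliation is needed on either reading.

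**Little depends on it.** The variable is exploratory and lies outside the Hochberg family, so no confirmatory conclusion rests on it. Protocol 12.2 promises that SAP departures will be discussed in the study report. Both are fair and keep the point minor; a departure missing from SAP 2.2 is, however, easier to overlook in the report.

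**The size is assumed.** This also stands. The 25% figure needs the smallest SD together with the largest q; at an SD of 3 days the inflation is 2% to 3%. The sample-loss conversion applies to a comparison of means, while the SAP also allows non-parametric tests. Correlation between A and S would change the figures.

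**Conclusion.** The definitions differ, the change is not listed in SAP 2.2, and the protocol-defined variable has no analysis. These conclusions rest on the text alone. The cost in precision is modest and only illustrative: about 2% to 25% more variance under the assumptions stated in the working. The point is minor.

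Three stronger readings are tempting, and the documents do not support them:

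- **That the comparison is biased.** Over all randomised patients it is not. Only the transferred subgroup lacks guaranteed balance, and the SAP text and table list conflict on whether that subgroup or the ITT set is used.
- **That every stay is lengthened, or all of labour is counted.** SAP item 7 uses dates, so a woman who arrives and delivers on the same calendar day gains nothing.
- **That the loss of power is large.** A doubling of the variance would need pre-delivery time to vary as much as the stay after delivery. A 0/1-day shift has an SD of at most 0.5 day, and the documents give nothing to support a larger one.

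**What to change.** In SAP 3.3.6.3.1 item 7, define the stay as hospital discharge date minus date of delivery, following Protocol 12.10.1.3.1 item 7, and use one name for it here and in 1.10.2.4. If the arrival-based duration of hospitalisation is still wanted, present it as description only. Record any retained departure, with its reason, in SAP 2.2. State one analysis population so that 3.3.6.3.2.2.4 and Table 14.2.5.5.2 agree.

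The cost is a few lines of SAP text and one changed start variable. Delivery times are collected at Visit 1 and the discharge date at Visit 6 (Protocol 8.2.1 and 8.2.6), so no new data are needed.
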